4.2.2 Complete Remission Rate and Duration (IRRC-assessed)

The complete remission rate (CRR) is defined as the number of subjects with a BOR of CR according to the 2007 revised International Working Group Criteria for Malignant Lymphoma, based on IRRC assessment, divided by the number of treated subjects.

To further characterize CRR, the duration of CR will also be evaluated in subjects with objective response of CR. Duration of CR is defined as the time from first documentation of CR (the date of first negative FDG-PET scan or the date of first documentation of no disease involvement in the bone marrow (if required), whichever occurs later) to the date of initial objectively documented progression as determined using the 2007 IWG criteria or death due to any cause, whichever occurs first. Censoring will be applied as per DOR definition.

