#### **5.4.3.5 PET scan**

A baseline PET scan is required for each treated subject. An additional PET scan is required to confirm a CR.

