### **8.3.2 Secondary Endpoint(s)**

The first secondary objective will be measured by the DOR based on IRRC assessment. DOR is defined as the time from first remission (CR or PR) to the date of initial objectively documented progression as determined using the 2007 IWG criteria or death due to any cause, whichever occurs first. For subjects who neither progress nor die, the DOR will be censored on the date of their last evaluable tumor assessment. Subjects who start subsequent therapy without a prior reported progression will be censored at the last evaluable tumor assessments prior to initiation of the subsequent anticancer therapy. This endpoint will only be evaluated in subjects with objective response of CR or PR.

[figure not shown]
The second secondary objective will be measured by the CRR based on IRRC assessment. The CRR is defined as the number of subjects with a BOR of CR according to the 2007 IWG criteria, divided by the number of treated subjects. The BOR is defined similarly as above. The duration of CR will only be evaluated in subjects with BOR of CR and is defined as the time from first documentation of CR (the date of first negative FDG-PET scan or the date of first documentation of no disease involvement in the bone marrow (if required), whichever occurs later) to the date of initial objectively documented progression as determined using the revised 2007 IWG criteria for malignant lymphoma or death due to any cause, whichever occurs first. Censoring will be applied as per DOR definition.

The third secondary objective will be measured by PR rate based on IRRC assessment. It is defined as the number of subjects with a BOR of PR according to the 2007 IWG criteria, based on IRRC assessment, divided by the number of treated subjects. The duration of PR will only be evaluated in subjects with BOR of PR and is defined as the time from first documentation of PR to the date of initial objectively documented progression as determined using the 2007 IWG criteria or death due to any cause, whichever occurs first. Censoring will be applied as per DOR definition.

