### **CR (Complete Remission)**

The designation of CR requires the following:

1. Complete disappearance of all detectable clinical evidence of disease and disease-related symptoms, if present before therapy.
2. a. Typically [F] fluorodeoxyglucose (FDG)-avid lymphoma: in patients with no pretreatment positron emission tomography (PET) scan or when the PET scan was positive before therapy, a post-treatment residual mass of any size is permitted as long as it is PET negative.
3. b. Variably FDG-avid lymphomas/FDG avidity unknown: in patients without a pretreatment PET scan, or if a pretreatment PET scan was negative, all lymph nodes and nodal masses must have regressed on computed tomography (CT) scan to normal size ( $\leq 1.5$  cm in their greatest transverse diameter for nodes  $> 1.5$  cm before therapy). Previously involved nodes that were 1.1 to 1.5 cm in their long axis and  $> 1.0$  cm in their short axis before treatment must have decreased to  $\leq 1.0$  cm in their short axis after treatment.
4. The spleen and/or liver, if considered enlarged before therapy on the basis of a physical examination or CT scan, should not be palpable on physical examination and should be considered normal size by imaging studies, and nodules related to lymphoma should disappear. However, determination of splenic involvement is not always reliable because a spleen considered normal in size may still contain lymphoma, whereas an enlarged spleen may reflect variations in anatomy, blood volume, the use of hematopoietic growth factors, or causes other than lymphoma.
5. If the bone marrow was involved by lymphoma before treatment, the infiltrate must have cleared on repeat bone marrow biopsy. The biopsy sample on which this determination is made must be adequate (with a goal of  $> 20$  mm unilateral core). If the sample is indeterminate by morphology, it should be negative by immunohistochemistry. A sample that is negative by immunohistochemistry but demonstrates a small population of clonal lymphocytes by flow cytometry will be considered a CR until data become available demonstrating a clear difference in patient outcome.

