4 ENDPOINTS

4.1 Primary endpoint ORR (IRRC-assessed)

The primary objective will be measured by the primary endpoint of IRRC-assessed ORR. It is defined as the number of subjects with a best overall response (BOR) of CR or PR, according to the 2007 IWG criteria (see [Table 4.1-1](#)), divided by the number of treated subjects. The final analysis of the primary endpoint will occur at least 12 months after the last enrolled subject's first dose of study therapy. The BOR is defined as the best response designation recorded between the date of first dose and the date of initial objectively documented progression per the 2007 IWG criteria or the first subsequent therapy date per IRRC, whichever occurs first.

The first subsequent therapy date per IRRC is determined by the IRRC based on non-palliative radiotherapy, local tumor treatment, systemic anti-cancer therapy and Stem Cell Transplant with a start date on or after the first study therapy date.

For subjects without documented progression or subsequent therapy, all available response designations will contribute to the BOR determination. For purposes of analysis, if a subject receives one dose and discontinues the study without assessment or receives subsequent therapy prior to assessment, this subject will be counted in the denominator (as non-responder).

The IRRC-assessed objective response will be further characterized by the time to response (TTR). TTR is defined as the time from first dosing date to the date of the first response (PR or CR), as assessed by the IRRC.

Table 4.1-1: 2007 IWG Response Criteria for Malignant Lymphoma

Response	Definition	Nodal masses	Spleen, Liver	Bone marrow
CR	Disappearance of all evidence of disease	(a) FDG-avid or PET positive prior to therapy; residual mass of any size permitted if PET negative (b) Variably FDG-avid or PET negative; regression to normal size on CT	Not palpable, nodules disappeared	Infiltrate cleared on repeat biopsy; if indeterminate by morphology, immunohistochemistry should be negative

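### The start date for duration of CR names only PET and marrow, so read literally it can precede CR and, in a narrow subset, the first dose

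*SAP*

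**What the plan says.** SAP 4.2.2 gives the origin in words: "Duration of CR is defined as the time from first documentation of CR". A parenthesis then turns this into dates: "the date of first negative FDG-PET scan or the date of first documentation of no disease involvement in the bone marrow (if required"), with the later of the two governing. Protocol 8.3.2 has the same construction, "the time from first documentation of CR (the date of first negative FDG-PET scan" and so on, and restricts the analysis: "The duration of CR will only be evaluated in subjects with BOR of CR". Best overall response is limited in SAP 4.1 to the "best response designation recorded between the date of first dose and the date of initial objectively documented progression" or subsequent therapy.

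The CR criteria (Protocol Appendix 2, SAP Table 4.1-1) ask for more than PET and marrow. Clinical evidence of disease and related symptoms must be gone, and the spleen and liver must be normal with nodules resolved. There is also a CT condition for one group: "if a pretreatment PET scan was negative, all lymph nodes and nodal masses must have regressed on computed tomography (CT) scan to normal size". If the pretreatment PET was positive, a residual mass of any size is acceptable once it is PET negative.

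On PET timing, Protocol 5.4.3.5 states: "A baseline PET scan is required for each treated subject". Protocol Table 5.1-1 places screening imaging in the 28 days before first dose. After that, PET is required only to confirm a CR. Entry depends on CT/MRI-measurable disease (Protocol 3.3.1, criterion 2c), not on a positive PET. A repeat marrow is needed for CR only if the marrow was involved at screening (Protocol 5.4.5).

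**The concern.** The parenthesis is the only operational date in the definition, so it is what a programmer is likely to code. It has two gaps. It has no post-baseline limit, although every subject has a PET before treatment. It also leaves out components that the plan itself requires before CR can be called. Either gap can put the start of the interval before the state it is meant to measure. Leaving out a required condition can only move the start earlier, so any error lengthens duration of CR.

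At stake are the Kaplan-Meier median and range for duration of CR, a named secondary endpoint. In some subjects the recorded value could also exceed their DOR or PFS, which is logically impossible.

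Duration of PR (SAP 4.2.3) has no such parenthesis and does not have this problem.

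**Working it through.** The plan states no figure for duration of CR, so there is nothing to reproduce on this endpoint. The primary test (27 of 90 responders, about 87% power, recomputed as 86.6%) does not use this date.

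**Inputs**
- Start rule: SAP 4.2.2, Protocol 8.3.2.
- Baseline PET between day -28 and day -1: Protocol 5.4.3.5 and Table 5.1-1.
- CT/MRI on Day 1 of Weeks 9, 17, 25 and 33, each ± 1 week: Protocol Table 5.4.1-1.
- Duration = last date - first date + 1; 1 month = 30.4375 days: SAP 8.

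**Step 1. Compare the CR criteria with the start rule.**

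| CR component | Needed for CR | In the start rule |
|---|---|---|
| Negative PET | Yes (on-study PET confirms CR) | Yes, but not limited to post-baseline |
| Marrow cleared | If involved at screening | Yes, and the later date governs |
| CT regression to normal size | Only if baseline PET negative | No |
| Spleen/liver normal, nodules gone | Yes | No |
| Clinical disease and symptoms gone | Yes | No |

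Two groups follow.
- (a) Baseline PET negative and no marrow date required: the first negative PET is the screening scan.
- (b) Baseline PET positive: CT size is not a condition, so the gap is spleen/liver and clinical findings only. It matters only if a PET was negative before those were met.

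**Step 2. Excess in group (a).** Day 1 of Week w falls 7 × (w - 1) days after first dose. For a PET done k days before first dose, excess = 7 × (w - 1) + k, with k from 1 to 28.

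| CR first met | 7 × (w - 1) | Excess, k = 1 | Excess, k = 28 |
|---|---|---|---|
| Week 9 | 56 | 57 days (1.9 months) | 84 days (2.8 months) |
| Week 17 | 112 | 113 days (3.7 months) | 140 days (4.6 months) |
| Week 25 | 168 | 169 days (5.6 months) | 196 days (6.4 months) |
| Week 33 | 224 | 225 days (7.4 months) | 252 days (8.3 months) |

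The ± 1 week visit window widens the Week 9 range to 57 - 7 = 50 through 84 + 7 = 91 days, and the Week 33 range to 218 through 259 days.

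**Step 3. Worked example (dates assumed).** Baseline PET negative on day -28, marrow not involved, progression 364 days after first dose.
- PFS = 364 + 1 = 365 days (12.0 months).
- Literal duration of CR = 364 + 28 + 1 = 393 days (12.9 months).
- Duration from actual CR at Week 9 = 364 - 56 + 1 = 309 days (10.2 months).
- Duration from actual CR at Week 33 = 364 - 224 + 1 = 141 days (4.6 months), against the same literal 393.

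**Step 4. Ordering of endpoints.** PFS starts at first dose and DOR at the first CR or PR; all three end at progression or death. A start before first dose therefore makes duration of CR longer than both. In group (b) the start is on study, so PFS cannot be exceeded. DOR is exceeded only if no PR or CR had been recorded by the date of that PET.

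**The case against.** The strongest reply is that the text already excludes the worst case. The origin is the documentation of CR, and the parenthesis only says which test date supplies it. A screening PET cannot document CR in a subject who must have a CT/MRI lesion larger than 15 mm to enter, and response designations count only from first dose. This argument stands in part: a careful programmer would probably reject a pre-dose date. But the first-dose limit applies to the response designation, not to the PET date, and the only dated rule remains incomplete. The sentence permits the error without instructing it.

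A reader might also infer more than the documents support:
- **That every subject PET-negative at baseline starts before first dose.** The later of the two dates governs, so anyone with marrow involvement at screening waits for marrow clearance.
- **That CT is wrongly ignored throughout.** For subjects PET-positive before therapy, CT size is not a CR condition and its omission is correct.
- **That negative PETs will routinely come a visit or more ahead of CR.** No serial PET is scheduled; the 8- and 12-weekly schedule is CT/MRI. Appendix 2 also reserves PET in follicular lymphoma for cases with one or at most two residual masses that have regressed by more than half. The confirming PET will usually fall at or after the CT that suggested CR.
- **That the reported median will move materially.** The documents give neither a baseline PET-negative rate nor an expected CR rate, so this cannot be computed.

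The IRRC charter, which is not among the documents, may already settle the date of CR.

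**Conclusion.** The concern holds in a limited form. The dated start rule in SAP 4.2.2 and Protocol 8.3.2 does not match the plan's own definition of CR and, applied literally, gives a wrong date for some subjects. In group (a) the excess per subject is 57-84 days for CR at Week 9 and 225-252 days at Week 33, at nominal visits with a PET 1 to 28 days before first dose. In group (b) the documents do not allow the excess to be sized.

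How many subjects fall in either group is unknown and probably few. ORR, CRR, DOR, PFS and power do not change. Duration of CR is a descriptive secondary endpoint with no hypothesis test, so this is a minor point, worth correcting because the correction is cheap.

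**What to change.** In both SAP 4.2.2 and Protocol 8.3.2, replace the parenthesis with: *the first post-baseline date by which all IWG CR components required for that subject (PET; CT regression if baseline PET was negative; spleen/liver; clinical; marrow if involved at screening) are documented, per IRRC*. If a confirming PET or marrow falls between CT visits and is the last component met, its date is the start.

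Add a programming check that duration of CR does not exceed DOR in any subject, and query any case that fails.

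The cost is a minor revision of two documents, with no new assessments. Affected subjects will show a somewhat shorter duration of CR.

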4.2.3 Partial Remission Rate and Duration (IRRC-assessed)

The partial remission rate (PRR) is defined as the number of subjects with a BOR of PR according to the 2007 revised International Working Group Criteria for Malignant Lymphoma, based on IRRC assessment, divided by the number of treated subjects.

To further characterize PRR, the duration of PR will also be evaluated in subjects with objective response of PR. Duration of PR is defined as the time from first documentation of PR to the date of initial objectively documented progression as determined using the 2007 IWG criteria or death due to any cause, whichever occurs first. Censoring will be applied as per DOR definition.

4.2.4 Progression Free Survival (IRRC-assessed)

Progression free survival (PFS) is defined as the time from first dosing date to the date of the first documented progression, as determined by an IRRC according to the 2007 revised International Working Group Criteria for Malignant Lymphoma, or death due to any cause, whichever occurs first.

- Subjects who have no baseline tumor assessment will be censored at their first dosing date.

- Subjects who have baseline tumor assessment and who die without a reported progression will be considered to have progressed on the date of their death.
- Subjects who did not progress or die will be considered as not progressed and will be censored on the date of their last assessment.
- Subjects who did not have any on study assessments and did not die will be censored on the first dosing date.
- Subjects who started any subsequent anti-cancer therapy without a prior reported progression will be censored at the last assessment prior to or on their first subsequent therapy date.

Table 4.2.4-1: Censoring scheme used in primary analysis of PFS

Situation	Date of Progression or Censoring	Outcome
No baseline tumor assessments	First Dosing date	Not Progressed
No on study tumor assessments and no death	First Dosing date	Not Progressed
No progression per 2007 IWG criteria and no new anti-cancer treatment started	Date of last tumor assessment with no documented progression per the 2007 IWG criteria	Not Progressed
New anticancer treatment started without a prior reported progression per 2007 IWG criteria	Date of last tumor assessment prior or on the date of initiation of the subsequent anti-cancer therapy	Not Progressed
Progression per 2007 IWG criteria documented between scheduled visits or at scheduled visit without prior new anticancer treatment started	Date of the first documented tumor progression per the 2007 IWG criteria	Progressed
Death without progression per 2007 IWG criteria and without prior new anticancer treatment started	Date of death	Progressed

To further characterize PFS, progression by response to most recent prior systemic cancer therapy and progression by number of prior systemic cancer therapy lines may also be evaluated.

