The fourth secondary objective will be measured by IRRC-assessed PFS. It is defined as the time from first dosing date to the date of the first documented progression, as determined by an IRRC, or death due to any cause, whichever occurs first. Subjects who die without a reported progression will be considered to have progressed on the date of their death. Subjects who did not progress or die will be censored on the date of their last evaluable assessment. Subjects who did not have any on study assessments and did not die will be censored on the first dosing date. Subjects who started any subsequent anti-cancer therapy without a prior reported progression will be censored at the last evaluable assessment prior to initiation of the subsequent anti-cancer therapy.

The fifth secondary objective will be measured by investigator-assessed ORR. Investigator-assessed ORR is defined similarly as described for the primary endpoint above.

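### SAP 4.2.4 censors PFS at first dose for a treated subject with no baseline scan who dies before new therapy; protocol 8.3.2 and the SAP table's own death row count that death as an event

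*SAP*

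**What the plan says.** Protocol 8.3.2 gives these PFS rules:

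- Death: "Subjects who die without a reported progression will be considered to have progressed on the date of their death".
- Censoring at first dose, which applies only to survivors: "Subjects who did not have any on study assessments and did not die will be censored on the first dosing date".
- New therapy: "Subjects who started any subsequent anti-cancer therapy without a prior reported progression will be censored at the last evaluable assessment" before that therapy began.

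None of these depends on a baseline scan.

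SAP 4.2.4 opens with a definition in which death from any cause is an event. Its bullets then add a condition:

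- Bullet 1: "Subjects who have no baseline tumor assessment will be censored at their first dosing date".
- Bullet 2: "Subjects who have baseline tumor assessment and who die without a reported progression will be considered to have progressed on the date of their death".
- Bullet 3 covers survivors: "Subjects who did not progress or die will be considered as not progressed".

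In Table 4.2.4-1, row 1 (no baseline assessment) assigns the first dosing date and a not-progressed outcome. Row 2 (no on-study assessment) does the same but is limited to subjects who have not died; row 1 has no such limit. Row 3 reads "No progression per 2007 IWG criteria and no new anti-cancer treatment started" and censors at the last assessment. The final row reads "Death without progression per 2007 IWG criteria and without prior new anticancer treatment started" and assigns an event on the date of death, whether or not there was a baseline scan. No order of precedence among the rows is given.

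**The concern.** A missing baseline scan can make progression hard to judge, but it does not make a known date of death unknown. As written, the SAP discards an observed PFS event for a reason the protocol does not recognise. The analysis population is all treated subjects (protocol 8.2, SAP 6.3.1), so such a subject stays in the PFS analysis.

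The outputs affected are those in SAP 7.5.5: the median, the rates at 6, 9 and 12 months, and the split of events into death and progression. The disputed death would leave the event count and move to the table of censored subjects, where the only category that could hold it is the residual one under off-study. Two programmers could also code the same death differently, one following row 1 and the other the death row.

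**Working it through.** **1. The rules applied to one subject.** Take a treated subject with no baseline scan and no documented progression who dies before any new therapy.

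| Source | Outcome | Date |
|---|---|---|
| Protocol 8.3.2 | Event | Death |
| SAP 4.2.4, opening definition | Event | Death |
| SAP 4.2.4, bullets 1 and 2 | Censored | First dose |
| Table 4.2.4-1, row 1 | Censored | First dose |
| Table 4.2.4-1, row 3 | Censored | Last assessment, if any |
| Table 4.2.4-1, death row | Event | Death |

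**2. How far the overlap reaches.** Among subjects without progression, cross baseline scan, on-study scan, new therapy before death, and death (each yes or no). This gives 2 × 2 × 2 × 2 = 16 types.

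- Four types meet both a censoring row and the death row. All are deaths without prior new therapy.
- The two with a baseline scan overlap through row 3 only. Bullets 2 and 3 settle them as events.
- The two without a baseline scan meet row 1, row 3 and the death row. Bullets 1 and 2 settle them as censored, against the protocol.
- If only row 1 is edited, all four types still meet row 3 and the death row. A precedence statement is therefore needed as well.

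**3. Size.** The documents give no PFS figure to reproduce. The only stated power, about 87%, is for ORR and does not depend on PFS censoring. The sample size, n = 90, is from protocol 8.1. Assumptions not in the documents: k such deaths, a landmark PFS rate S under the protocol rule, and no other censoring before the landmark. Under the SAP bullets the rate is estimated from the other 90 − k subjects.

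*All k die before the landmark.* SAP rate = 90S/(90 − k), so the difference is kS/(90 − k), in percentage points:

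| k | S = 20% | S = 40% | S = 60% |
|---|---|---|---|
| 1 | 0.20/89 = +0.22 | 0.40/89 = +0.45 | 0.60/89 = +0.67 |
| 2 | 0.40/88 = +0.45 | 0.80/88 = +0.91 | 1.20/88 = +1.36 |
| 3 | 0.60/87 = +0.69 | 1.20/87 = +1.38 | 1.80/87 = +2.07 |

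*One death after the landmark.* SAP rate = (90S − 1)/89, so the difference is −(1 − S)/89: −0.90, −0.67 and −0.45 points for S = 20%, 40% and 60%. The direction depends on when the death falls.

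*Kaplan-Meier check.* In 1,500 simulated trials of 90 with assumed exponential medians of 4, 6, 9 and 12 months, one subject died on Day 60 or was instead censored on Day 1. Censoring raised the rate by 0.39 to 0.79 points at 6 months and 0.14 to 0.56 points at 12 months. This agrees with the algebra. If the other 89 have rate S₀, the difference is S₀/90; at 6 months a 4-month median gives 0.354/90 = 0.39 points and a 12-month median gives 0.707/90 = 0.79.

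*Scale.* The approximate 95% half-width is 1.96 × √(S(1 − S)/90): 8.3 points at S = 20% and 10.1 points at S = 40% or 60%. Three early deaths at S = 60% shift the rate by 2.07/10.1, about one fifth of the half-width.

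**The case against.** The best defence is that the SAP bullets form a deliberate pair, one for subjects without a baseline scan and one for those with it, and that row 1 matches the first. A programmer reading the whole section would know to censor. The SAP history for version 3.0 mentions clarifying the PFS censoring scheme. The affected group should be nearly empty, since measurable disease is an inclusion criterion and baseline CT or MRI and PET are required. PFS has no hypothesis or threshold, and the shift from one subject is far inside the confidence interval.

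The points on rarity and size stand, and they make this a minor correction. They do not remove the departure. The history entry does not declare one, and the bullets still conflict with the protocol, with the SAP's opening definition and with the death row.

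Two further objections concern the repair. First, row 1 would still overlap rows 3 to 5 for no-baseline subjects who do not meet the death row, for example a survivor with an on-study scan. That is true, but it is an existing ambiguity separate from this one. Second, no-baseline subjects would contribute follow-up only if they die, and a late death may stand in for progression that could not be assessed. That is a real asymmetry, but the protocol already accepts it for subjects with no on-study assessments, who are censored at first dose if alive and counted if they die.

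**Conclusion.** The SAP rule is wrong as written. It censors a death that protocol 8.3.2 counts, and the SAP's own definition and table do not support it consistently. The effect is zero if no treated subject without a baseline scan died before new therapy, and the documents do not give that number. If one did, a landmark PFS rate moves by less than one percentage point: up for a death before the landmark, down for one after it. Three early deaths would move it up by 0.69 to 2.07 points. These figures assume 90 subjects, a rate of 20% to 60% and no other censoring before the landmark. The primary ORR, its power and its decision rule are unaffected.

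**What to change.** In SAP 4.2.4:

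1. Add to row 1 of Table 4.2.4-1 and to bullet 1 the limit *except where the subject died with no earlier new anticancer treatment*. A subject with no scans who starts new therapy and later dies is then still censored at first dose. A bare no-death qualifier would leave that subject without a usable date, because row 4 needs an earlier assessment.
2. In bullet 2, remove the baseline-assessment condition and require instead that no new anticancer therapy came before the death.
3. Add under the table: *The death row takes precedence over rows 1 and 3.*

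With these edits, none of the 16 subject types meets a censoring row and the death row without a stated order, and censoring at new therapy is preserved. The cost is one table row, two bullets and one sentence, with no new data and no new output. The remaining overlaps of row 1 with rows 3 to 5 could be settled in the same revision.

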4.2 Secondary Endpoints

4.2.1 Duration of Response (IRRC-assessed)

Duration of response (DOR) is defined as the time from first response (CR or PR) to the date of initial objectively documented progression as determined using the 2007 revised International

Working Group Criteria for Malignant Lymphoma or death due to any cause, whichever occurs first. For subjects who neither progress nor die, the DOR will be censored on the date of their last evaluable tumor assessment. Subjects who start subsequent therapy without a prior reported progression will be censored at the last evaluable tumor assessments prior to or on the first subsequent therapy date per IRRC. This endpoint will only be evaluated in subjects with objective response of CR or PR. Ongoing responders are defined as responders who did not progress, did not die, are not off study and did not started a subsequent therapy.

Duration of Stable Disease will also be evaluated for subjects with SD as best response. Duration of SD is defined as the time between the first dose date to the date of the first documented progression, as determined by IRRC, or death due to any cause, whichever occurs first. Subjects who neither progress nor die will be censored at the same time they will be censored for the DOR analysis.

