6.3 Populations for Analyses

6.3.1 Analysis Populations

The following populations will be defined.

- **All enrolled subjects:** All subjects who signed an informed consent form and were registered into the IVRS.
- **All treated subjects:** All enrolled subjects who received at least one dose of nivolumab. This is the primary population for efficacy and safety.
- **All response evaluable subjects:** All treated subjects who have baseline and at least one on-study evaluable tumor measurement.
- **PK subjects:** All enrolled subjects with available serum time-concentration data from subjects dosed with nivolumab.
- **Immunogenicity evaluable subjects:** all treated subjects with baseline and at least one post baseline immunogenicity assessment.
- **All PD-L1 tested subjects:** All enrolled subjects who had a tumor tissue sample available for assessment of PD-L1 expression.
- **All PD-L1 evaluable subjects:** All treated subjects with quantifiable baseline PD-L1 expression
- **Biomarker subjects:** All treated subjects with available biomarker data.
- **Outcomes Research subjects:** all treated subjects who have an assessment at baseline (Visit 1 assessment prior to administration of drug) and at least 1 subsequent assessment (for EORTC QLQ-C30 and EQ-5D separately).

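### SAP 4.2.4 omits the protocol's condition that the last assessment used to censor PFS be evaluable, so PFS and DOR can be censored on different dates for the same subject

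*SAP*

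**What the plan says.** **Protocol 8.3.2, PFS.** With no event: "Subjects who did not progress or die will be censored on the date of their last evaluable assessment". With subsequent therapy and no prior progression, the subject "will be censored at the last evaluable assessment prior to initiation of the subsequent anti-cancer therapy". Both rules carry the evaluability condition.

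**SAP 4.2.4, PFS.** With no event: "Subjects who did not progress or die will be considered as not progressed and will be censored on the date of their last assessment". With subsequent therapy, the subject "will be censored at the last assessment prior to or on their first subsequent therapy date". In Table 4.2.4-1 the no-event row reads "Date of last tumor assessment with no documented progression per the 2007 IWG criteria". The subsequent-therapy row gives the last tumor assessment up to and including the start of new therapy, with no further qualifier. The condition appears in none of the four places.

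**SAP 4.2.1, DOR.** "For subjects who neither progress nor die, the DOR will be censored on the date of their last evaluable tumor assessment". The subsequent-therapy rule for DOR also keeps the word. Duration of CR and of PR (SAP 4.2.2 and 4.2.3) take the DOR censoring. Duration of stable disease runs from first dose to IRRC progression or death, and its censoring is tied to the DOR analysis.

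The SAP document history lists a clarification of the PFS censoring scheme at version 3.0. It gives no reason for leaving the condition out.

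**The concern.** A scan that cannot be evaluated does not show whether the disease has progressed. The protocol's PFS rule therefore ends follow-up at the last scan that could be evaluated. The SAP's rule, taken at its word, ends it at the last scan. A subject whose final scan was not evaluable then stays at risk for one more scan interval without a reading to support it.

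Two things are at stake. First, two programmers, one working from the protocol and one from the SAP, could obtain different PFS curves from the same data. Second, the SAP becomes inconsistent with itself. A responder can be followed longer for PFS than for DOR. A subject with a best response of stable disease can have two censoring dates for PFS and duration of stable disease, which share the same start and the same events.

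**Working it through.** **1. The plan's own figure.** The documents give no design figure for PFS. Their only one is about 87% power for ORR with 90 subjects, a null of 20% and a true rate of 35%. With at least 27 responders required, the exact binomial P(X ≥ 27 | n = 90, p = 0.35) is 0.866, so the figure reproduces. PFS censoring does not enter it.

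**2. Is the condition restored elsewhere in the SAP?** The nearest qualifier is the absence of documented progression in the no-event row. A scan that cannot be evaluated also documents no progression, so literally it passes. The subsequent-therapy row lacks even that qualifier. Elsewhere the SAP treats evaluability as a real restriction: the response-evaluable population is "All treated subjects who have baseline and at least one on-study evaluable tumor measurement".

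**3. Direction.** Event dates are the same under both rules; only some censoring dates move later. At each event time the Kaplan-Meier factor is 1 − d/n. If m ≥ 0 subjects remain at risk who would already have been censored under the protocol rule, it becomes 1 − d/(n + m), which is at least as large. The SAP estimate is therefore equal to or above the protocol estimate at every time. This needs no simulation.

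**4. Time added per affected subject.** From the tumor assessment schedule (SAP 2.1, Protocol Table 5.4.1-1) and the SAP's 30.4375 days per month, one trailing non-evaluable scan adds:
- 8-week phase: 8 × 7 / 30.4375 = 1.84 months
- 12-week phase: 12 × 7 / 30.4375 = 2.76 months
- after 2 years: 26 × 7 / 30.4375 = 5.98 months

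**5. Effect on the 12-month PFS rate.** The documents give no rate of non-evaluable scans, no expected PFS and no dropout rate, so every input here except the 90 subjects and the scan schedule is an assumption. Both rules were simulated with exponential PFS and administrative censoring spread uniformly over 12 to 30 months.

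*Central case* (median 11 months, 25% dropout per year, one trailing non-evaluable scan):

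| Subjects affected | Rise in 12-month PFS, points |
|---|---|
| 5% | about 0.1 |
| 10% | about 0.25 |
| 20% | about 0.5 |

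*Wider range* (medians 6, 11 and 18 months, 30% dropout by 12 months):

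| Subjects affected | One trailing scan, points | Two trailing scans, points |
|---|---|---|
| 5% | 0.10 to 0.15 | 0.24 to 0.35 |
| 10% | 0.21 to 0.31 | 0.51 to 0.84 |
| 20% | 0.41 to 0.69 | 0.99 to 1.73 |
| 30% | 0.66 to 0.97 | 1.56 to 2.77 |

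In the wider range the typical Kaplan-Meier median did not move at assumed medians of 6 and 11 months. At 18 months it moved by one visit, from 18.4 to 21.2 months, once 10% or more of subjects were affected. With nobody affected, the two rules coincide.

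**The case against.** The strongest reply is that the SAP does not mean what the literal reading makes of it. It nowhere says that assessments count whether or not they can be evaluated. PFS is defined by IRRC progression under the 2007 IWG criteria, so an assessment without documented progression can naturally be read as one where the IRRC applied those criteria and found none. Programmers may filter on evaluability anyway, and the IRRC charter, which is not available here, may settle what counts as an assessment. This stands in part: the literal reading is a risk, not an established practice. It is weaker for the subsequent-therapy row, and it does not explain why the word was kept for DOR.

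A reader might go further and infer that unreadable scans will be counted as progression-free, or that reported PFS will be biased upward. The documents do not support that. Protocol 5.9 says the core laboratory queries quality problems and requests repeat scans. That shows that such scans occur, but it is also a way of replacing them, and it does not show that they remain as a subject's last scan.

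The effect is also small beside other features of the estimate. In the central case the sampling standard deviation of 12-month PFS is about 5.6 points. Both rules give about 53% against a true 2^(−12/11) = 46.9%, because progression is dated at scans and none is scheduled between Weeks 45 and 57. This stands, and it limits the importance of the point without removing the conflict.

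Finally, inserting one word in four places would be incomplete. Neither document defines an evaluable assessment, and a subject whose only on-study scans are non-evaluable would have no clear censoring date. This stands too, and the fix below covers it.

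**Conclusion.** The SAP's PFS censoring rule departs from protocol 8.3.2 in both situations, without a stated reason, and does not match the SAP's own rule for DOR and duration of stable disease. Followed literally, it leaves PFS equal to or higher than under the protocol rule. That comparison is between the two rules. It does not establish that the reported PFS will be wrong, which depends on how many censored subjects end on a non-evaluable scan and on how the rule is programmed.

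Under the central assumptions, with 5 to 20% of subjects affected, the 12-month rate rises by roughly 0.1 to 0.5 points. The largest figure found, 2.8 points, needs 30% of subjects to end on two non-evaluable scans. PFS is a secondary endpoint, summarized descriptively without a test. ORR, its 27-of-90 rule and its power are untouched. This is a minor wording conflict, worth correcting because the correction is cheap.

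**What to change.** In SAP 4.2.4:

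1. Insert 'evaluable' before 'assessment' in the no-event and subsequent-therapy bullets, and make the same insertion in the two matching rows of Table 4.2.4-1.
2. Change the bullet and row for subjects with no on-study assessment to refer to no evaluable on-study assessment, so that subjects with only non-evaluable scans and no death are censored at first dose.
3. State that an evaluable assessment is one with an IRRC time-point response other than not evaluable.

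If the omission was deliberate, record it instead as a departure from the protocol, with the reason and a sensitivity analysis under the protocol rule.

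The cost is a short SAP edit with no new data. PFS may become marginally less favourable.
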